8.2.2. PROMIS Fatigue-7a

The PROMIS Fatigue 7-items Short Form (PROMIS Fatigue Short Form 7a) contains 7 items evaluating fatigue-related symptoms (ie, tiredness, exhaustion, mental tiredness, and lack of energy) and associated impacts on daily activities (ie, activity limitations related to work, selfcare, and exercise) (Ameringer 2016). PROMIS Fatigue Short Form 7a has a recall period of past 7 days. Compared to the fatigue scale of PROMIS-29, PROMIS Fatigue Short Form 7a provides additional information to evaluate severity of fatigue. The raw total score is converted into a standardized score with a mean of 50 and a SD of 10 (T-Score). The standardized T-score is reported as the final score for each participant.

8.2.3. Work Productivity and Activity Index for Crohn's disease (WPAI-CD)

The WPAI-CD is a validated instrument created as a patient-reported quantitative assessment of the amount of absenteeism, presenteeism, and daily activity impairment attributable to CD (Reilly 2008). The WPAI-CD consists of 6 questions to determine employment status, hours missed from work due to CD, hours missed from work for other reasons, hours worked, the degree to which CD affected work productivity while at work, and the degree to which CD affected activities outside of work. Higher scores indicate greater impairment.

8.3. Healthcare Resource Utilization Data

CD-related hospitalizations, surgeries, emergency room visits, medication use, and physician visits will be used to evaluate healthcare resource utilization, which are important considerations when assessing ideal therapy selection in CD patients.

8.4. Safety Assessments

Safety evaluations will include the assessment of AEs, clinical laboratory tests (hematology and chemistry), vital signs, screening physical examination, concomitant medication review, and monitoring for hypersensitivity reactions, occions site reactions, suicidal ideation and behavior by the C-SSRS, and early detection of active TB.

Evaluations of safety and tolerability will occur at time points specified in the SoA (Section 1.3).

Adverse events will be reported and followed by the investigator as specified in Section 8.5, Adverse Events, Serious Adverse Events, and Other Safety Reporting, and Appendix 4: Adverse Events, Serious Adverse Events, Product Quality Complaints, and Other Safety Reporting: Definitions and Procedures for Recording, Evaluating, Follow-up, and Reporting.

Any clinically relevant changes occurring during the study must be recorded on the Adverse Event section of the eCRF.

Any clinically significant abnormalities (ie, SAEs) persisting at the end of the study/early withdrawal will be followed by the investigator until resolution or until a clinically stable condition is reached.

The study will include the following evaluations of safety and tolerability according to the time points provided in the Schedule of Activities.

8.4.1. Physical Examinations

A complete, detailed physical examination, including height and weight, will be performed as per local practice standards for eligibility assessment. While assessment of the participants for safety and efficacy requires a full physical examination at screening and at Week 152, a directed physical exam for abdominal mass and fistulas, (perianal and other) will be performed at all visits. Participants will be instructed to remove shoes and outdoor apparel and gear prior to measurements for height and weight.

Physical examination data will not be included in the study database as such; abnormal physical examination findings are to be reported as AEs.

8.4.2. Vital Signs

Temperature, pulse/heart rate, respiratory rate, and blood pressure will be assessed at the Week 0, 48, and 152 visits. Vital signs should be recorded before and approximately 30 minutes after the study intervention during the main treatment period through Week 48, or if the participant reports symptoms.

Study participants who are trained to self-inject (or will have a trained caregiver to inject) study intervention at home will be trained to perform self-evaluation for site reactions and reporting of AEs after administering study interventions at home. Vital signs will only be assessed at the study site when study participants receive study intervention administration at the study site.

Vital signs data, which are considered source data, are not to be entered into the study database or analyzed. Abnormal vital signs are to be recorded as AEs.

8.4.3. Clinical Safety Laboratory Assessments

Blood samples for serum chemistry and hematology will be collected as noted in Appendix 2: Clinical Laboratory Tests. The investigator must review the laboratory results, document this review, and record any clinically relevant changes occurring during the study in the AE section of the eCRF. The laboratory reports must be filed with the source documents.

8.4.4. Pregnancy Testing

Pregnancy testing will consist of a serum pregnancy test at screening and urine testing at on-site study visits. Additional serum or urine pregnancy tests may be performed, as determined necessary by the investigator or required by local regulation, or if a participant suspects pregnancy, to establish the absence of pregnancy at any time during the participation in the study.

8.4.5. Suicidal Ideation and Behavior Risk Monitoring

The C-SSRS defines 5 subtypes of suicidal ideation and 4 possible suicidal behaviors, as well as non-suicidal self-injurious behavior and completed suicide. It will be used as a screening tool to prospectively evaluate suicidal ideation and behavior in this study, as part of a comprehensive evaluation of safety. The C-SSRS is an investigator-administered questionnaire and will be generally conducted on the electronic clinical outcomes assessment (eCOA) device provided to the site. The C-SSRS will be provided in the local languages in accordance with local guidelines.

Two versions of it will be used in this study: the 'Baseline/Screening' version of the C-SSRS will be conducted during the screening visit and the 'Since Last Visit' version of the C-SSRS will be completed at Week 0 and all other site visits through the end of the study.

At screening, the C-SSRS will be the first assessment performed, before any other study procedure. At all subsequent visits, the C-SSRS will be performed according to the assessment schedule and should be performed after other PROs but before any other study procedure. The investigator or trained study-site personnel will interview the participant in a private place and complete the C-SSRS.

At the conclusion of each assessment, the trained personnel administering the C-SSRS will determine the level of suicidal ideation or behavior, if any. They will then determine the next course of action if any level of suicidal ideation or behavior is reported. The participant should not be released from the site until the C-SSRS has been reviewed by the investigator and the participant's risk has been assessed and follow-up determined, as appropriate.

At screening (within the last 6 months) and Week 0, participants with a C-SSRS rating of Suicidal Ideation with Intention to Act ("Ideation level 4"), Suicidal Ideation with Specific Plan and Intent ("Ideation level 5"), or suicidal behavior (actual suicide attempt, interrupted suicide attempt, aborted suicide attempt, or preparatory behaviors for making a suicide attempt), must be determined to not be at risk by the investigator based on an evaluation by a mental health professional (eg, psychiatrist, psychologist, or appropriately trained social worker or nurse) in order to be randomized.

Participants with C-SSRS ratings of Wish to be Dead ("Ideation level 1"), Non-Specific Active Suicidal Thoughts ("Ideation level 2"), Active Suicidal Ideation with Any Methods (Not Plan) without Intent to Act ("Ideation level 3") or non-suicidal self-injurious behavior must be determined not to be at risk by the investigator in order to be randomized. Any questions regarding eligibility of such participants should be discussed with the medical monitor or designee.

For each assessment after Week 0, the following actions should be taken, if applicable:

- No suicidal ideation or behaviors (including self-injurious behavior without suicidal intent): No further action is needed.
- Suicidal ideation levels 1-3 or non-suicidal self-injurious behavior: Participant risk is assessed by the investigator.

• Suicidal ideation levels 4 or 5 or any suicidal behavior: Participant risk assessed and referral to a mental health professional.

Interruption or the discontinuation of study intervention should be considered for any participant who reports Suicidal Ideation with Intention to Act ("Ideation level 4"), Suicidal Ideation with Specific Plan and Intent ("Ideation level 5"), or suicidal behavior (actual suicide attempt, interrupted suicide attempt, aborted suicide attempt, or preparatory behaviors for making a suicide attempt) on a post-baseline C-SSRS assessment and who is deemed to be at risk by the investigator based upon evaluation by a mental health professional. If a participant can be adequately treated with psychotherapy and/or pharmacotherapy then the participant, at the discretion of the investigator, may be continued with treatment if agreed to by the medical monitor or designee. Discussion of such participants with the medical monitor or designee is required (Section 7.1).

Any C-SSRS finding, which in the opinion of the investigator is new or considered to be a worsening and clinically significant, should be reported on the AE eCRF. The completed C-SSRS and AE data will not be reconciled with each other.

8.4.6. Site Reactions

A study intervention site reaction is any adverse reaction at a SC study intervention site. The sites will be evaluated for reactions at on-site visits and any site reaction will be recorded as an AE.

8.4.7. Hypersensitivity Reactions

Before any administration of study intervention at the study site, appropriately trained personnel and medications (eg, antihistamines, injectable epinephrine) must be available to treat hypersensitivity reactions, including anaphylaxis. All participants must be alert for or, when on site, observed carefully for signs and symptoms of a hypersensitivity reaction (eg, urticaria, pruritus, angioedema, wheezing, dyspnea, or hypotension). If a mild or moderate hypersensitivity reaction is observed, acetaminophen, nonsteroidal anti-inflammatory drugs, and/or diphenhydramine may be administered. Participants who experience serious adverse reactions related to an infusion must strongly be considered to be discontinued from further study intervention administrations.

In the case of a severe hypersensitivity reaction (eg, anaphylaxis), SC aqueous epinephrine, corticosteroids, respiratory assistance, and other proper resuscitative measures are essential and must be available at the study site where the infusions are being administered.

Participants who experience reactions suggestive of serum sickness (resulting in symptoms such as myalgia and/or arthralgia with fever and/or rash that are not representative of signs and symptoms of other recognized clinical syndromes) occurring 1 to 14 days after an infusion of study intervention, should be discontinued from further study intervention administrations. Note that these symptoms may be accompanied by other events including pruritus; facial, hand, or lip edema; dysphagia; urticaria; sore throat; and headache.

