Hypersensitivity reactions, including serious hypersensitivity reactions and anaphylaxis.	Serious hypersensitivity reactions including anaphylaxis have been reported in postmarketing experience with guselkumab	 Participants with known allergy, hypersensitivity, or intolerance to guselkumab will be excluded from the study (Section 5.2). All participants must be alert for or, when on site, observed carefully for signs and symptoms of a hypersensitivity reaction (eg, urticaria, itching, hives) (Section 8.4.7). Any participant who develops a serious hypersensitivity reaction such as anaphylaxis must discontinue study intervention (Section 7.1).
Malignancy	The preponderance of preclinical data suggests that blockade of endogenous IL-23 would not be detrimental and may in fact be beneficial in tumor immunosurveillance and host protection; however, a risk of malignancy cannot be excluded.	 Those participants who currently have a malignancy or have a history of malignancy within 5 years prior to screening (with exceptions noted in Section 5.2) will be excluded from the study. Additionally, participants who have a history of lymphoproliferative disease, including lymphoma, a history of monoclonal gammopathy of undetermined significance or signs and symptoms suggestive of possible lymphoproliferative disease, such as lymphadenopathy or splenomegaly will be excluded from the study (Section 5.2). During the conduct of the study, participants will undergo regular clinical monitoring including routine safety laboratory assessments to evaluate any changes in health status that may indicate a possible malignancy. Participants who develop a malignancy during the study (with the exception of no more than 2 localized basal cell skin cancers that are treated with no evidence of recurrence or residual disease) will be discontinued from study intervention (Section 7.1).
Liver injury	An SAE of 'toxic hepatitis' was reported in a participant in the ongoing Phase 2/3 guselkumab CD who received guselkumab CO at Weeks 0, 4, and 8, and at Week 12. This event may represent drug induced liver injury	During the conduct of the study, liver function tests will be monitored at regular intervals in accordance with regulatory guidance (FDA 2009). In addition, the induction doses evaluated in this clinical program will not exceed

CNTO1959 (guselkumab)	Clini	ical Protocol CNTO1959CRD3007 Amendment 1

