7. DISCONTINUATION OF STUDY INTERVENTION AND PARTICIPANT DISCONTINUATION/WITHDRAWAL

7.1. Discontinuation of Study Intervention

A participant's study treatment should be discontinued if:

• The investigator or the medical monitor believes that for safety reasons (eg, an AE) it is in the best interest of the participant to stop treatment.

- The participant becomes pregnant or plans a pregnancy within the study period or within 12 weeks after the last study intervention administration.
- The participant meets **ANY** of the following TB related conditions:
 - A diagnosis of active TB is made.
 - A participant has symptoms suggestive of active TB based on follow-up assessment questions and/or physical examination or has had recent close contact with a person with active TB and cannot or will not continue to undergo additional evaluation.
 - A participant undergoing evaluation has chest imaging with evidence of current active TB and/or a positive IGRA test result, unless active TB can be ruled out and appropriate treatment for latent TB can be initiated prior to the next administration of study intervention and continued to completion.
 - A participant receiving treatment for latent TB discontinues this treatment prematurely or is noncompliant with the therapy.
- The participant has a serious adverse reaction that is related to an bronchospasm with wheezing and/or dyspnea that requires ventilatory support OR that results in symptomatic hypotension with a decrease in systolic blood pressure >40 mm Hg or blood pressure <90/60 mm Hg. In general, discontinuation of study intervention administration must be considered for participants who develop non-serious, but severe
- The participant develops a malignancy including squamous cell skin cancer. Consideration may be given to allow participants to continue to receive study intervention if they develop ≤2 basal cell skin cancers that are adequately treated with no evidence of residual disease.
- The initiation of the following protocol-prohibited medications at any time during the study as listed in Section 6.8.2.
- A serious opportunistic infection occurs.
- The participant (or the participant's representative) withdraws consent (or assent) for further administration of study intervention.

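### Protocol 8.4.7 only asks that stopping be considered after a serious reaction to an infusion, whereas 2.3.1 makes the stop mandatory and every study intervention is subcutaneous

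*Protocol*

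**What the plan says.** Section 2.3.1 of the Protocol (Risks for Study Participation) lists the mitigation for hypersensitivity: "Any participant who develops a serious hypersensitivity reaction such as anaphylaxis must discontinue study intervention (Section 7.1").

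Section 8.4.7 (Hypersensitivity Reactions) begins by requiring trained staff and medication to be on hand before any on-site administration. Three later sentences refer to infusions:

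- Serious reactions: "Participants who experience serious adverse reactions related to an infusion must strongly be considered to be discontinued from further study intervention administrations".
- Resuscitation: the measures "must be available at the study site where the infusions are being administered".
- Serum sickness: participants with suggestive symptoms "occurring 1 to 14 days after an infusion of study intervention, should be discontinued from further study intervention administrations".

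Table 1 in Section 6.1 gives one route, subcutaneous, for all three interventions: blinded guselkumab, matching placebo and open-label guselkumab after cross over.

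Section 7.1 (Discontinuation of Study Intervention) introduces its list with "study treatment should be discontinued if". Its first bullet applies when the investigator or medical monitor "believes that for safety reasons (eg, an AE) it is in the best interest of the participant to stop treatment". A later bullet covers a serious adverse reaction. Part of it is blacked out, and the readable part refers to "bronchospasm with wheezing and/or dyspnea that requires ventilatory support OR that results in symptomatic hypotension".

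**The concern.** Section 2.3.1 tells ethics committees and regulators how the anaphylaxis risk is controlled: a participant with a serious hypersensitivity reaction gets no more study drug. Section 8.4.7 tells the site what to do. If it leaves the decision open, the stated mitigation is not what the site is instructed to carry out.

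The word infusion adds a second problem. A stopping rule triggered by an infusion has no trigger in a trial that gives only subcutaneous doses. The likely origin is text carried over from an intravenous protocol, but that is an inference. What is at stake is the decision on the next dose after a serious or delayed reaction, including a dose the participant takes at home.

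**Working it through.** No arithmetic applies. The check is a comparison of the current text, using only words that are printed in full.

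**Inputs**

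| Place | Event covered | Action | Route condition |
|---|---|---|---|
| Protocol 2.3.1 | Serious hypersensitivity reaction | Mandatory stop | None |
| Protocol 8.4.7, serious reactions | Serious adverse reaction | Strong consideration of a stop | Infusion |
| Protocol 8.4.7, serum sickness | Suggestive symptoms, days 1 to 14 | Should stop | Infusion |
| Protocol 8.4.7, resuscitation | Severe reaction | Measures available on site | Infusion |
| Protocol 6.1, Table 1 | Not applicable | Not applicable | Subcutaneous, all three interventions |

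**Step 1: route.** Section 8.4.7 refers to infusions three times, and two of these are the trigger for a stop. Table 1 plans no infusion of study drug, and the rationale in Section 2.2.2 also says guselkumab will be given subcutaneously. Intravenous dosing is mentioned only for other studies. The word infusion is printed in full in 8.4.7, so it is not an effect of redaction.

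**Step 2: anaphylaxis after a subcutaneous dose.** Sections 2.3.1 and 8.4.7 do not cover identical sets of events, but both aim at anaphylaxis, so it serves as the test case.

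- Under 2.3.1, study drug stops.
- Under 8.4.7 read literally, the sentence does not apply, because nothing was infused.
- Under 8.4.7 with infusion read as administration, the investigator must give stopping strong consideration, and may then continue and still comply with the sentence.

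Neither reading of 8.4.7 gives the result stated in 2.3.1. Correcting the route alone would leave the difference in strength.

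**Step 3: serum sickness after a subcutaneous dose.** Read literally, the stop in 8.4.7 does not apply. With infusion read as administration, it works as intended. Here the only fault is the route.

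**Step 4: resuscitation measures.** The first sentence of 8.4.7 already requires staff and medication for any on-site administration. The infusion wording in the later sentence does little harm, but should be corrected with the rest.

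**The case against.** The strongest reply is that no investigator would be misled. Section 8.4.7 opens by referring to any administration at the site, and both of its stops end by ruling out further administrations of study drug. Section 2.3.1 is unambiguous. Section 7.1 has a serious-reaction bullet and a general safety bullet, and serious events are reportable within 24 hours under Section 8.5.1. Most readers would take infusion to mean injection. All of this stands and is why the severity is minor. It does not settle the matter: reading infusion as injection leaves the weaker verb in place, and the general bullet in 7.1 depends on a judgement, whereas 2.3.1 states an automatic stop.

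Several stronger readings are tempting, but the documents do not support them.

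- *Three competing strengths of stop, counting the should in 7.1.* That word introduces every stop in the 7.1 list, including active tuberculosis, pregnancy and malignancy. The liver injury row of 2.3.1 also pairs a must with a reference to 7.1. A must in the risk table beside the should of 7.1 is the protocol's general style. The three sections also differ in the events they cover.
- *Section 8.4.7 moves serious reactions into a tier that 7.1 reserves for non-serious ones.* This relies on the words "In general, discontinuation of study intervention administration must be considered for participants who develop non-serious, but severe", which come from the partly blacked-out bullet and break off at a gap. The bullet's full structure cannot be read.
- *The plan has no other stop for serum sickness.* No readable 7.1 bullet names it, but blacked-out text cannot be counted as missing.
- *The frequency of home dosing measures the problem.* Home doses would be equally frequent under perfect wording.

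**Conclusion.** Section 8.4.7 is wrong as written, with minor severity. It conflicts with 2.3.1 on whether study drug must stop after a serious hypersensitivity reaction, and it ties two stops and one readiness requirement to a route the trial does not use. The conclusion rests on intact text in 2.3.1, 8.4.7 and Table 1, and on the two sections overlapping for anaphylaxis. It assumes nothing about the hidden words in 7.1.

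The size is qualitative: three infusion references against no planned infusions, and one mandatory stop reduced to a consideration. The first bullet and the readable serious-reaction bullet of 7.1 limit the practical harm. No effect on power, alpha or results is claimed. Actual exposure was small, since SAP Section 1 reports that the study was discontinued with four participants enrolled.

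**What to change.** Change Section 8.4.7 only, in three places:

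1. Serious reactions: *Participants who experience a serious hypersensitivity reaction (eg, anaphylaxis) after any study intervention administration, on site or at home, must be discontinued from further study intervention (Section 7.1).*
2. Resuscitation: *at the study site where study intervention is administered*.
3. Serum sickness: *occurring 1 to 14 days after any study intervention administration (on site or at home)*.

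The first replacement is limited to hypersensitivity so that it matches 2.3.1. Other serious reactions remain under the general safety bullet of 7.1. Sections 2.3.1 and 7.1 need no change for this point.

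The cost is wording in one protocol amendment, with no added visits, tests or staff.
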